2.3 Exercise and Breast Cancer Risk

Multiple epidemiologic studies have evaluated the association between exercise and breast cancer risk. A recent review of 18 cohort and 23 case-control studies found that observations from 26 of these studies including 108,031 breast cancer cases demonstrated that exercise (both occupational and leisure-time) is associated with a 30% reduction in breast cancer risk (9). Further supporting a reduced risk associated with exercise, a significant graded dose-response relationship was found in 16 of the studies (9). Moderate non-vigorous exercise can increase insulin sensitivity and improve dyslipidemia even without change in body weight (10, 11). Thus exercise can serve to counter the negative influences associated with obesity and breast cancer pathogenesis.

[figure not shown]
[figure not shown]
2.4 Ginseng has both anti-cancer and anti-diabetic effects

Studies in [name] laboratory have characterized an extract of the American ginseng root that inhibits proliferation of human breast cancer cells in culture and in animal models. Studies from this and other laboratories have shown that American ginseng and ginsenosides may inhibit cancer cell proliferation by inducing gene and protein expression of the cell cycle regulatory protein p21, thus arresting tumor cell cycle progression (12), by inducing cancer cell apoptosis through activation of caspase-3 protease via a *bcl-2*-insensitive pathway and by sensitizing multidrug-resistant tumor cells to chemotherapy (13, 14). Together, these data indicate that the individual ginsenosides may inhibit cancer cell proliferation via different mechanisms of action and in a concentration-dependent manner.

The treatment of human breast cancer cell lines MCF-7 or MDA-MB-231 with a water-extract of powdered North American ginseng root produced a significant decrease in cell proliferation in a dose-dependent and estrogen receptor-independent manner (15). Moreover, in athymic nude mice inoculated with either MCF-7 or MDA-MB-231 cells, treatment with a 1% solution of American ginseng extract in lieu of drinking water produced a $\geq 50\%$ reduction in tumor size when compared to water-only controls (16). Recent laboratory studies have determined that ginseng also significantly enhances the efficacy of doxorubicin and tamoxifen on breast cancer cell proliferation *in vitro*, and on tumor growth in nude mice *in vivo*.

Further studies from this laboratory and others, have elucidated the ginsenoside components in ginseng that exhibit the anti-tumor effects (17, 18). Ginsenosides are saponin glycosides unique to and the major biologically active components in ginseng. Over 20 different ginsenosides have been identified and, based on their structural differences; the ginsenosides found in American and Asian ginseng have been categorized into two main classifications: 20(S)-protopanaxadiol and 20(S)-protopanaxatriol. The 20(S)-protopanaxadiol group contains the ginsenosides (i.e., ginsenosides Rc, Rg3, Rh2) that have been shown to have the most potent anti-cancer activity (18) and do not exhibit the estrogenic activity of ginseng extract (19, 20) and other ginsenosides (21, 22). Figure 2 shows the effects of various ginsenosides on cell proliferation. Results clearly show that these ginsenosides inhibit cancer cell proliferation (4), induce cancer cell death (13,

12), and prevent cancer metastasis (23). Thus, it appears that ginsenosides Rc, Rg3, and Rh2 may be responsible for the therapeutic effects of American and Asian ginseng in experimental studies. Ginsenosides Rc and Rh2 have been shown to have the most potent anti-cancer activity (see Figure 1), and do not exhibit the estrogenic activity of ginseng ethanol extracts (21).

Recently, ginseng extract (13) and the ginsenosides Rg3 and Rh2 (23) were shown to inhibit cell proliferation and disrupt MAP kinase signaling in a dose-dependent manner in human breast and prostate cancer cells, respectively. Ginseng and ginsenosides also have metabolic effects which may reduce carcinogenesis via the inflammatory and hyperinsulinemic states associated with the metabolic syndrome. American ginseng, in doses of 1 to 3 grams, taken 40 minutes before a glucose challenge test reduced postprandial glycemia in both diabetic and non-diabetic subjects (24, 25). Moreover, 20(S)-protopanaxatriol inhibits inducible nitric oxide synthase and COX-2 expression through inactivation of NFκB in RAW264.7 macrophages that were stimulated with endotoxin lipopolysaccharide (26).

An advantage of ginseng therapy is that it remains potent following oral administration. Pharmacokinetic studies have revealed that following oral administration of ginseng, the ginsenosides are absorbed and pass through the system unmetabolized (i.e., Rg1, Rd, Re, Rb1, Rb2, Rc) (27); are hydrolyzed and conjugated with fatty acids into metabolites that become more metabolically stable and retain their activity, and/or are deglycosylated and degraded into metabolites that are either more potent anti-cancer compounds (i.e., protopanaxadiol, protopanaxatriol, IH-901, Compound K or M1) (28, 29), or have no reported anti-cancer activity (i.e., Rh1, Rf1). Interestingly, ginsenosides Rb1 and Rc can be metabolized into the potent anti-cancer ginsenosides Rg3 and Rh2 by acid environment and intestinal flora (30). Ginsenoside Rg3 is rapidly metabolized by the gut into Rh2 and protopanaxadiol (26), both of which possess greater anti-tumor activity than Rg3.

Our existing study, the Surrogate Endpoints and Lifestyle Factors (SELF) trial, has as its goal to analyze the prevalence in women seeking risk assessment for breast cancer, of insulin resistance, central obesity, and proliferative changes in mammary ductal cells, and determine whether these potential surrogate endpoint biomarkers (SEBs) have a positive correlation with breast cancer risk. The findings will be used to refine the relevant biomarkers and perform a power analysis for a 5-year clinical trial with breast cancer as an endpoint. Once these biomarkers are validated, other candidate prevention agents for breast cancer could be incorporated into future trials. Significant correlations between SEB and breast cancer incidence will allow clinicians to identify women who can effectively lower their breast cancer risk, potentially with American ginseng. Therefore we will establish a base of comparison between breast cancer patients and participants in the SELF study by collecting anthropometric data (height, weight, body composition, waist-hip ratio), dietary history, exercise habits, and insulin resistance blood panel (HOMA index, leptin, ghrelin, and adiponectin) and calculated 5 year risk of breast cancer (Gail score) in participating breast cancer patients. Contingent on an observed antiproliferative effect of ginseng on tumor or surrounding normal breast tissue in treated breast cancer patients or on the other surrogate markers of breast cancer risk, a breast cancer prevention trial involving exercise with or without ginseng supplementation will be designed.

2.5 Gelatin Encapsulated Standardized Lyophilized Water-Extract of American Ginseng root derived from *Panax quinquefolius*, L. (LEAG)

Asian ginseng (*Panax ginseng*) and its close relative American ginseng (*Panax quinquefolium*) are perennial aromatic herbs that are widely used in Asian medicine. Ginseng root is used as a tonic thought to increase the body's resistance to stress and fatigue, to increase endurance under heavy physical activity, and to improve well-being in age-related debilitation. Most of the ginseng consumed, even in Asian populations, is American ginseng, and the majority of American ginseng is grown and processed in Wisconsin, with quality and standardization overseen by the Ginseng Board of Wisconsin. Furthermore, in Asian medicine, Asian ginseng (*Panax ginseng*) and American ginseng (*Panax quinquefolium*) are common components in herbals used for cancer prevention and treatment. Indeed, retrospective studies have shown that patients who consumed ginseng on a regular basis experienced cancers at a reduced rate (31), however, breast cancer was not considered. Ginseng has been used medicinally for over 2000 years and there are no substantiated serious adverse effects, and few, if any, non-serious adverse effects. The World Health Organization lists ginseng as a traditional medicine with very low toxicity (32, 33). Clinical trials have also demonstrated an anti-hyperglycemic action of American ginseng. These studies utilized capsules containing dried, ground Ontario-grown *P. quinquefolius* L. root. The ground AG root preparation had an onset of action of 40 minutes (24). They found no significant increase in anti-hyperglycemic action after 40 minutes (24) and no significant increase in anti-hyperglycemic action using 1 gram versus 3 gram dosing.

LEAG is a standardized preparation of lyophilized water-extract of American ginseng root in 250-mg gelatin capsules. The ginseng was purchased through the Ginseng Board of Wisconsin and the lyophilized extract has been certified for percentage of each and total ginsenoside content and screened for safe levels of minerals, metals, and pesticides by ConsumerLab.com, a leading testing service company of dietary supplements (Appendix E).

2.6 Rationale

Studies that target primary prevention are difficult due to the large number of subjects and many years of follow-up that are required. Our strategy is to evaluate the effect of oral ginseng on several proliferative tumor associated biomarkers, as well as inflammatory and obesity related biomarkers.

There is precedent for the use of biomarkers in short-term neoadjuvant therapy of breast cancer. The IMPACT trial compared the preoperative use of tamoxifen with anastrozole alone or in combination in postmenopausal women (n=330) with primary breast cancer (34). Immunohistochemical levels of the proliferation marker Ki-67, estrogen receptor (ER), progesterone receptor (PR), and HER-2 neu were assessed at diagnosis, 2 weeks, and 12 weeks. A reduction in Ki-67 was seen at 2 weeks in the majority of patients (93%, 85%, and 84% of those treated with anastrozole, tamoxifen, and combination, respectively). The percent reduction of Ki-67 by treatment group paralleled the tumor response rate and disease-free survivals of these different treatments, confirming the value of Ki-67 as a biomarker of tumor response to therapy

(35). Because the proliferation marker Ki-67 has been shown to be reduced by as little as two weeks of neoadjuvant therapy (35), we hypothesize that proteins that regulate the cell cycle, inflammation, and cell death can show alteration in expression within one cell cycle and can be detectable in tumor specimens after 5 or more days of treatment.

Targets for cancer prevention are being sought among the numerous regulatory molecules involved in cellular proliferation, differentiation, and DNA repair. A morphological description of breast carcinogenesis is currently based on a model of progression from hyperplasia to DCIS to invasive carcinoma. This is based on both analogy to the colon cancer hyperplasia-dysplasia model (for which many of the genes involved in the progression have been identified) and on surgical and autopsy studies. In a study comparing benign proliferative lesions occurring in the same breast with invasive cancer, 50% of the hyperplastic lesions and 80% of the ductal carcinoma in situ (DCIS) shared at least one LOH with the adjacent cancer (36). In the breast, the process of intraepithelial neoplasia can be shown to contain a spectrum of morphologic findings ranging from ductal hyperplasia to atypical ductal hyperplasia to DCIS. The earliest precursor lesions rarely show overt markers of malignancy such as p53 mutation, but they do differentially express cell cycle regulatory proteins. Immunohistological and RT-PCR studies of proliferative ductal epithelial lesions in breast tissue associated with resected carcinoma show increased cyclin D1 expression, which mediates cell cycle progression, in 72% of DCIS and 27% of atypical ductal hyperplasia (37, 38). In contrast, cyclin D2, which regulates cell cycle arrest, is abundant in finite-lifespan human mammary epithelial cells (HMEC) and benign breast tissue, but is decreased or undetectable in 87% of breast cancer cell lines and primary tumors (39). Recently, cyclooxygenase-2 (COX-2) staining was found to be increased not only in DCIS but in the stroma and benign breast tissue surrounding the lesion (40). COX-2 modulates prostanoid production in the direction of stimulating epithelial proliferation and is upregulated in colon, breast, and other cancers (41). COX-2 upregulation may also be associated with diabetes. Human endothelial cells cultured in high glucose conditions show increased COX-2 mRNA and protein and increases in oxidative stress (42). Though cell proliferation and regulation are obviously important, they are no longer the only targets of therapy. Mechanisms of tumor spread and angiogenesis are also highly studied,

Angiopoietin plays a physiologic role in angiogenesis and lymphangiogenesis and is involved in the maintenance of vascular function and integrity⁵². Four members (Ang 1, Ang 2, Ang 3, and Ang 4) make up this family with 2 receptors, Tie 1 and Tie 2. An increasing number of studies show that angiopoietin-2 correlates with tumor angiogenesis, tumor stage, lymph node invasion and length of survival^{51,52,53,54,55,56}. Many cancers, including lung, breast, neuroendocrine, colorectal, and melanomas have associations of high angiopoietin-2 and stage of disease; therefore, signifying high potential as a biomarker of stage and/ or metastasis. This potential is not only due to its broad association with cancer in general but also its ease of analysis in serum. Agents which inhibit angiopoietin's actions would, therefore, also have high potential for use in cancer treatment.

The present study was designed to explore the changes brought about by LEAG in breast cancer tumors and surrounding normal breast epithelial cells. Various tumor biomarkers, as well as

inflammatory mediators, will be examined in tissue following LEAG treatment. Positive trends and/or results in this study will be the basis for future studies utilizing LEAG.

3.0 PATIENT SELECTION

3.1 Eligibility Criteria

1. Patients with a cytologically confirmed diagnosis of breast cancer with a biopsy showing invasive or non-invasive breast cancer (DCIS) at least 1.0 cm greatest diameter on imaging (biopsy must have been performed within 6 months of screening visit).
2. Surgical patients, undergoing lumpectomy, subtotal or total mastectomy.
3. Age ≥ 18 years of age.
4. Female.
5. Patients must have tissue blocks available from diagnostic biopsy.
6. Negative pregnancy test, medical history of surgical sterilization, or 1 year post-menopausal. The effects of LEAG on the developing human fetus at the recommended therapeutic dose are unknown. For this reason women of child-bearing potential must agree to use adequate contraception (hormonal or barrier method of birth control; abstinence) prior to study entry and for the duration of study participation.
7. Patient must be willing to forgo surgery for a minimum of 5 days.
8. The ability and willingness to sign a written consent.
9. Patients currently being treated for hypertension must be on a stable dose of medication for the past 30 days.
10. Diabetic patients must be well controlled (HbA1c < 8.5 within past 60 days or documented fasting blood glucose < 140 mg/dl for three consecutive days). Known diabetics who have experienced episodes of symptomatic hypoglycemia in the last 6 months are also considered poorly controlled and will be excluded from study participation.
11. ECOG status of ≤ 2 or Karnofsky $\geq 60\%$ (Appendix F).

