1.0 OBJECTIVES

1.1 Primary Objectives

Analyze biomarker *in vivo* response of breast cancer tumors and surrounding normal breast epithelial cells to preoperative treatment with gelatin encapsulated lyophilized water-extract of American Ginseng root (LEAG).

- 1.1.1 The diagnostic core biopsy will be compared to the operative specimen for effects on the following proliferative and tumor biomarkers: immunohistochemistry for ER, PR, Ki67, cyclin D1, COX-2.

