12.0 STUDY CALANDER

	Screening	Study Visit One	Follow-up Phone Call	Study Visit Two	Study Visit Three
Informed Consent	X				
LEAG ^A		X-----X			
Surgery				X	
Demographics	X				
Medical History and Physical	X				X
Vital Signs	X	X		X	X
Concurrent Medications	X	X-----X			
Height	X				
Weight	X				
Body mass Index		X			
Performance Status	X	X		X	X
Waist Hip Ratio		X			
Body Composition		X			
Gail Model Risk Assessment		X			
NCI Dietary Questionnaire		X			
Tecumseh Questionnaire		X			
Minnesota Questionnaire		X			
Fasting Blood Draw for Laboratory Studies ^B		X		X	
Platelet Function Assay-100 ^G		X		X	
Adverse Event Evaluation		X-----X			
Radiologic Evaluation ^C	X				
Tissue Collection	X			X	
Pregnancy test ^D	X				
HbA1c/ Blood glucose ^E	X				
Diary ^F					
Capsule Count ^H				X	

A: LEAG must be taken for a minimum of 5 days and no more than 14 days. Final dose to be taken day prior to surgery. Patients are required to keep a Ginseng medication diary.

B: Patients must be NPO after midnight. Draw 40 cc of blood from a vein into vacutainer tubes: 6mL in EDTA, 6mL in Na Heparin, 5mL in clot activator tube, and 24mL in serum tubes. Refrigerate serum tubes at 4°C until centrifugation for serum collection and storage.

C: All radiologic evaluations must be completed within 6 weeks of treatment. (mammogram, ultrasound, and MRI are acceptable)

D: Urine pregnancy test for patients of child bearing potential.

E: Only required in diabetic patients. If an HbA1c has not been conducted within 60 days, a fasting blood glucose finger stick of < 140 mg/dl for 3 consecutive days will be allowed as a substitute for verification of control.

F: Patient must be given a diary for blood pressures and/ or blood glucose by finger stick if they are being treated for hypertension or have been diagnosed with diabetes, respectively. Diaries need only be kept while patient is actively on LEAG (5-14 days). Diaries to be returned to research nurse on day of surgery.

G: The Platelet Function Assay-100 test is only conducted on the first 5 patients enrolled. Draw 2 – 2.7mL citrate tubes.

H: Patients are required to keep a Ginseng medication diary. The diary and pill bottle should be returned the day of surgery.

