13.0 DEFINITIONS OF MEASUREMENT

13.1 Diagnostic Disease Parameters for Inclusion in Study

- Measurable disease

Measurable lesions are defined as those that can be accurately measured in at least one dimension (longest diameter to be recorded) as ≥ 0.5 cm with conventional techniques (mammography, MRI, ultrasound). All tumor measurements must be recorded decimal fractions of centimeters.

- Non-measurable disease

All lesions < 0.5 cm using mammography, MRI or ultrasound, are considered non-measurable disease.

All measurements should be taken and recorded in metric notation using a ruler or calipers. All baseline evaluations should be performed as closely as possible to the beginning of treatment and never more than 6 weeks before the day of surgery.

- Mammogram

Lesions on mammogram films are acceptable as measurable lesions when they are clearly defined and surrounded by fatty breast tissue.

- Ultrasound (US)

Ultrasound measurement of tumor is an adjunct to the clinical measurement of palpable breast tumors and lymph nodes and to the mammographic measurement of tumor. When the clinically palpable lesion is larger than the US image, the clinical measurement is primary.

- Magnetic Resonance Imaging (MRI)

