16.0 STATISTICAL CONSIDERATIONS

Statistical Methods

High variability among tumors in the patient population is anticipated. Each patient will serve as her own control; pre-treatment biopsy tissue will be compared to post-treatment surgical tissue. Descriptive statistics including the mean, median, range, standard deviation, interquartile range, skewness, and kurtosis will be calculated for each measure. Paired t-tests, or Wilcoxon signed-rank tests, depending on the distributional characteristics of the variables, will be used to assess changes in biomarkers from biopsy to surgery. In order to examine the inter-relationships between the anthropometric data, the cytological markers, serum ginsenoside concentrations, and a panel of inflammatory serum proteins, data visualization techniques will be employed. Correlation coefficients will be used to summarize linear relationships between continuous measures. Regression techniques will be used to model nonlinear relationships. All statistical procedures will be performed in consultation with the Division of Statistics and Research Consulting at SIU School of Medicine.

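### The tissue baseline may be a biopsy taken up to 6 months before screening, and the paired analysis takes no account of the biopsy-to-surgery interval

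*Combined protocol and SAP*

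**What the plan says.** Section 1.1 sets the primary tissue comparison: "The diagnostic core biopsy will be compared to the operative specimen for effects on the following proliferative and tumor biomarkers", namely ER, PR, Ki67, cyclin D1 and COX-2. No new pre-treatment biopsy is planned. Section 3.1, item 5, states "Patients must have tissue blocks available from diagnostic biopsy", and Section 5.2.1 draws the baseline tissue from those blocks.

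Section 3.1, item 1, sets the age limit of that tissue: "biopsy must have been performed within 6 months of screening visit". The count runs to screening. I found no maximum from screening to first dose, or from biopsy to surgery. LEAG is then taken for 5 to 14 days (Section 5.3.1).

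Section 16.0 makes each patient her own control and plans paired t-tests or Wilcoxon signed-rank tests, which "will be used to assess changes in biomarkers from biopsy to surgery". It has no interval term, stratum, sensitivity analysis or summary. Its planned correlations and regressions concern anthropometric data, cytological markers, ginsenoside levels and serum proteins, not time.

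Two 6-week rules appear elsewhere. Section 13.1 says "All baseline evaluations should be performed as closely as possible to the beginning of treatment and never more than 6 weeks", counted back from surgery. Calendar footnote C in Section 12.0 says "All radiologic evaluations must be completed within 6 weeks of treatment". Section 9.1 requires blood for the inflammatory mediators and HOMA index within 2 weeks of treatment.

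**The concern.** In a single-arm paired design, the test attributes to LEAG everything that changes between the two specimens. When the first specimen was taken shortly before dosing, the untreated part of the interval is small. When it was taken months earlier, most of the interval is untreated, and any change in that time enters the estimate as response, or cancels a real response.

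The tissue baseline has the loosest window of the baselines named above, although it carries the primary comparison. Section 2.6 expects treatment to alter these classes of protein within one cell cycle. That does not show that they drift without treatment, but it sits uneasily with assuming stability over months. Section 7.2 monitors concomitant medication only from enrollment, so the period between biopsy and enrollment is also less well documented.

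The result matters for what follows. Section 2.4 makes the design of a prevention trial contingent on an observed antiproliferative effect or an effect on other surrogate markers. Section 2.6 makes positive trends the basis for further LEAG studies.

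**Working it through.** The plan gives no alpha, power, effect size, SD or drift, so it has no figure of its own to reproduce.

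**1. Interval at the permitted limit.** Inputs: 6 months (Section 3.1, item 1), taken as 182 days; 5 to 14 days of LEAG (Section 5.3.1); no gap between screening and first dose, which is the shortest case.

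- 5 days of LEAG: interval = 182 + 5 = 187 days; share on LEAG = 5/187 = 2.7%.
- 14 days of LEAG: interval = 182 + 14 = 196 days; share on LEAG = 14/196 = 7.1%.
- Any gap between screening and first dose lowers both shares.

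**2. Comparison with a 42-day interval.** 187/42 = 4.5 and 196/42 = 4.7, so the permitted interval is about four and a half times as long. In pairs of at most 42 days, LEAG would cover at least 5/42 = 11.9% (5 days) or 14/42 = 33.3% (14 days). Such pairs can still contain up to 42 − 5 = 37 or 42 − 14 = 28 untreated days.

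**3. Sensitivity of the paired test to drift (assumed inputs).** Suppose LEAG has no effect and the marker shifts between specimens by a mean of d SDs of the paired difference, averaged over all patients. The two-sided 5% paired t statistic is then noncentral t with n − 1 degrees of freedom and noncentrality d√n.

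| Mean drift d | Rejection rate, n = 25 | Rejection rate, n = 50 |
|---|---|---|
| 0 | 5% | 5% |
| 0.1 | 8% | 11% |
| 0.2 | 16% | 28% |
| 0.3 | 30% | 55% |
| 0.4 | 48% | 79% |
| 0.5 | 67% | 93% |

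These are mean shifts over the whole sample. If only one patient in five had a long interval and the rest did not drift, a mean of 0.2 SD would need a shift of 0.2/0.2 = 1.0 SD in that fifth (ignoring the added spread). The table shows how sensitive the test is; it does not estimate the effect of the 6-month window.

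**4. What a regression on the interval can recover.** Regress the paired change on interval x, with mean m and SD s.

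- With x centred at m, the intercept equals the raw mean change, so the average drift remains in it.
- The predicted change at x₀ has a standard error larger than that of the prediction at m by √(1 + ((x₀ − m)/s)²): √2 = 1.4 times at one SD below the mean, √5 = 2.2 times at two SDs below.
- x₀ = 0 lies outside the data, because every interval is at least 5 days, and it relies on linear drift.

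The useful outputs are therefore the slope and the predicted change at a short interval that occurs in the data.

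**5. Scope of Section 13.1.** The phrase about all baseline evaluations taken alone would include the biopsy. The sentence just before it reads "All measurements should be taken and recorded in metric notation using a ruler or calipers", and the section defines measurable lesions on mammography, MRI and ultrasound. The calendar lists radiologic evaluation and tissue collection as separate rows, and footnote C is attached only to the first. Section 3.1, item 1, gives the biopsy its own window.

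**The case against.** A reader might infer that Section 13.1 contradicts Section 3.1 outright, since a biopsy up to 6 months before screening cannot also be "never more than 6 weeks before the day of surgery". The context does not support this. Section 13.1 probably concerns lesion measurement, and imaging, blood and biopsy each have their own window. What stands is an ambiguity of scope that one sentence from the sponsor would settle.

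The permitted extreme may also be rare. Patients are newly diagnosed, study drug is dispensed against a scheduled surgery date, and imaging must be recent. That is plausible, but the documents give no interval distribution and the plan does not ask for one, so it cannot be checked.

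The drift size is assumed, and nothing ties 0.2 to 0.3 SD to a particular interval. This is correct, and the rejection rates must be read that way. The study is also exploratory, so a type I error argument carries less weight. That lowers the stakes, but bias in the estimated change still matters when that change informs later trials.

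The strongest objection is that no adjustment can replace an untreated group. That stands too. An interval covariate can show an association between change and time; it cannot isolate LEAG.

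Finally, not every marker is affected. The synopsis lists angiopoietin 2 among the primary evaluations, and Section 9.1 measures it in serum before and after LEAG. The point is limited to the five tissue markers.

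**Conclusion.** The point holds for the tissue markers. The baseline may precede screening by 6 months, no biopsy-to-surgery limit is stated, and the planned tests ignore the interval in a design with no untreated group. At the permitted limit LEAG covers about 3% to 7% of the time between specimens, assuming 182 days for 6 months and no delay from screening to first dose.

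Three stronger conclusions are not supported. The documents do not establish a clear contradiction between Sections 3.1 and 13.1, and they do not settle whether Section 13.1 covers the biopsy. They do not show that the false-positive rate is 16% to 55%; that range follows only from an assumed mean drift of 0.2 to 0.3 SD across all patients and n of 25 to 50, and drift the other way could hide an effect. Nor do they show that long intervals are typical.

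This is a cheap improvement to the analysis rather than a flaw that invalidates the trial.

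**What to change.** In Section 16.0:

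- Report the distribution of biopsy-to-surgery days (median, quartiles, range, and number of pairs at 6 weeks or less).
- Pre-specify a sensitivity analysis that repeats the primary paired tests in pairs with a short interval, for example 6 weeks or less.
- As an exploratory check, regress the paired change on the interval. Report the slope and the predicted change, with confidence intervals, at a stated short interval within the data, not the mean-centred intercept.
- State that these steps detect or reduce interval-related drift. They do not isolate the LEAG effect or remove fixed differences between a core biopsy and a surgical specimen.

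Separately, the sponsor should state whether the 6-week sentence in Section 13.1 covers the biopsy, and reconcile it with Section 3.1, item 1.

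Cost: analysis wording, with no added patients or procedures. The biopsy date is needed to check Section 3.1, item 1, and surgery is a study visit, so both dates should be obtainable. The downsides are a smaller n in the short-interval subset and an imprecise regression estimate at 25 to 50 patients. If marker results have already been examined when this is added, the report should say so.
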